**Table 2: Dose Modification Algorithms for Potential Treatment-Related Adverse Events**

AE Terms & Descriptions	Dose Modification Algorithms
Hypertension	
(A). Asymptomatic and persistent SBP of $\geq 140$ and $<170$ mmHg, or DBP $\geq 90$ and $<110$ mmHg, or a clinically significant increase in DBP of 20 mmHg (but still below 110 mmHg).	Step 1. Continue investigational product (IP) at the current dose. Step 2. Adjust current or initiate new antihypertensive medication(s). Step 3. Titrate antihypertensive medication(s) during next 2 weeks as indicated to achieve well-controlled blood pressure (BP). If BP is not well-controlled within 2 weeks, consider referral to a specialist and go to scenario (B).
(B). Asymptomatic SBP $\geq 170$ mmHg, or DBP $\geq 110$ mmHg, or failure to achieve well-controlled BP within 2 weeks in scenario (A).	Step 1. Consider reducing or interrupting IP, as clinically indicated. Step 2. Adjust current or initiate new antihypertensive medication(s). Step 3. Titrate antihypertensive medication(s) during next 2 weeks as indicated to achieve well-controlled BP. Step 4. Once BP is well-controlled, restart IP dose-reduced by 200 mg if IP was interrupted.
(C). Symptomatic hypertension or recurring SBP $\geq 170$ mmHg, or DBP $\geq 110$ mmHg, despite modification of antihypertensive medication(s)	Step 1. Interrupt IP Step 2. Adjust current or initiate new antihypertensive medication(s). Step 3. Titrate antihypertensive medication(s) during next 2 weeks as indicated to achieve well-controlled BP. Referral to a specialist for further evaluation and follow-up is also recommended. Step 4. Once BP is well-controlled, restart IP dose-reduced by 200 mg.

(D). Refractory hypertension unresponsive to above interventions.	Discontinue IP and continue follow-up per protocol.
Prolongation of QTc Interval: If the QTc is prolonged, the ECG should be manually read to ensure accuracy of the reading. The values below refer to manually-read ECGs.	
QTc $\geq$ 480 < 500 msec	Continue IP; monitor as clinically indicated.
QTc $\geq$ 500 msec	Discontinue IP and continue follow-up per protocol.
Proteinuria	
UPC <3	Continue Pazopanib at the current dose; monitor as clinically indicated

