UPC $\geq$ 3 or 24-h urine protein $\geq$ 3g	
Step 1. Interrupt IP.
 
Step 2. Weekly UPC or 24-hr urine protein monitoring until UPC is <3 or 24-hr urine protein is <3 grams. Then restart Pazopanib dose-reduced by 200 mg.
 
Step 3. If UPC <math>\geq</math>3 or 24-h urine protein <math>\geq</math> 3g recurs, repeat steps 1 and 2.
 
Step 4. If UPC <math>\geq</math>3 or 24-hr urine protein <math>\geq</math>3 recurs and the Pazopanib dose can no longer be reduced, discontinue Pazopanib and continue follow-up per protocol.

Hemorrhage /Bleeding: Investigate and document underlying etiology of the bleeding	
Grade 1	
For hemoptysis, interrupt Pazopanib and contact Chief Study Physician to discuss whether further treatment with Pazopanib is appropriate.
 
For other Grade I haemorrhage/bleeding events, continue Pazopanib at the current dose; monitor as clinically indicated.

Grade 2	
Step 1. If pulmonary or GI bleed (other than hemorrhoidal bleeding), discontinue IP and continue follow-up per protocol. Otherwise, interrupt IP until the AE resolved to <math>\leq</math> Grade 1.
 
Step 2. Restart IP; consider reducing dose and monitor as clinically indicated.

Grade 3 or 4, or Recurrent $\geq$ Grade 2 event after dose interruption/reduction.	Discontinue IP and continue with follow-up per protocol.
Venous Thrombosis (DVT, PE)	
Grade 2	Continue IP at the current dose; monitor as clinically indicated
Grade 3	
Step 1. Interrupt IP.
 
Step 2. Initiate and monitor anticoagulation as clinically indicated.
 
Step 3. Resume IP at reduced dose only if all of the following criteria are met:
 
 
• The subject must have been treated with anticoagulant at the desired level of anticoagulation for at least one week.
 
• No Grade 3 or 4 or clinically significant Grade 2, hemorrhagic
 

[figure not shown]

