	
events have occurred while on anticoagulation treatment.
 
Subject should be monitored as clinically indicated during anticoagulation treatment and after resuming study treatment. When treating with warfarin, international normalized ratio (INR) should be monitored within three to five days after any change in IP dosing (eg, re-initiating, escalating/de-escalating, or discontinuing IP), and then at least weekly until the INR is stable. The dose of warfarin (or its derivatives) may need to be adjusted to maintain the desired level of anticoagulation

Grade 4 and/or PE	Discontinue IP and continue follow-up per protocol.
Arterial Thrombosis/Ischemia	
Any Grade	Discontinue IP and continue follow-up per protocol.
Thrombocytopenia: Investigate and document underlying cause	
Grade 1 or 2	Continue IP with current dose; monitor as clinically indicated.
Grade 3 or 4	
Step 1. Interrupt IP until toxicity resolves to <math>\leq</math> Grade 2.
 
Step 2. Restart IP dose-reduced by 200 mg and monitor as clinically indicated.
 
If no recovery to <math>\leq</math> Grade 2 or recurrent Grade 3 or 4 thrombocytopenia, discontinue IP and follow-up per protocol.

Anemia: No specific dose reduction rules are indicated for anemia unless due to hemorrhage or bleeding as noted above.	
Palmar-plantar Erythrodysesthesia Syndrome	
Grade 1 Minimal skin changes or dermatitis without pain (erythema, oedema, hyperkeratosis)	Continue IP at present dose
Grade 2 Skin changes with pain; limiting instrumental activities of daily living (ADLs) (peeling, blisters, oedema, bleed, hyperkeratosis)	
 
1. Hold IP
 
2. Treat as clinically appropriate
 
3. Upon resolution to Level 1 or better restart IP with a dose reduction to 400 mg
 
4. If recurrent consider a further dose reduction to 200mg or discontinuation
 

Grade 3 Severe skin changes with pain and limiting self care ADLs	Discontinue IP
Other Clinically Significant Adverse Eventsb	
Grade 1	Continue IP; monitor as clinically indicated.
Grade 2 or 3, if clinically significant	
Step 1. Interrupt IP until toxicity resolves to <math>\leq</math> Grade 1.
 
Step 2. Restart IP dose-reduced by 200 mg and monitor as clinically indicated.

Grade 4	Discontinue IP and continue follow-up per protocol.

- Well-controlled BP defined as SBP <140 mmHg and mean DBP <90 mmHg.

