**Table 4: NCI CTCAE Version 4.0 criteria for defining diarrhea**

Toxicity Grade	Diarrhea (includes diarrhea of small bowel or colonic origin and/or ostomy diarrhea)
1	Increase of <4 stools/day over baseline; mild increase in ostomy output compared to baseline

2	Increase of 4-6 stools/day over baseline; moderate increase in ostomy output compared to baseline
3	Increase of $\geq 7$ stools/day over baseline; incontinence; hospitalization indicated; severe increase in ostomy output compared to baseline; limiting self-care activities of daily living
4	Life threatening consequences, urgent intervention indicated
5	Death

Uncomplicated diarrhea is considered mild to moderate and is defined as CTCAE Grade 1 to 2 with no complicating signs or symptoms.

Complicated diarrhea is severe and defined as CTCAE Grade 3 or 4 or Grade 1 or 2 with one or more of the following signs or symptoms: severe cramping,  $\geq$  Grade 2 nausea/vomiting, decreased performance status, fever, sepsis, Grade 3 or 4 neutropenia, obvious bleeding, dehydration.

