### **Management Guidelines**

#### **Uncomplicated diarrhea of CTCAE Grade 1 or 2:**

- Hydration: have subject drink 8 to 10 large glasses (approximately 2 litres) of clear non-caffeinated liquids a day (e.g., broth or electrolyte-containing sports drinks).
- If Grade 2 diarrhea, consider dose reduction of investigational products.
- Dietary modifications: have subject stop all lactose-containing products and eat frequent, small meals
- Pharmacologic intervention using loperamide:
  - Begin loperamide at initial dose of 4 mg followed by 2 mg every 4 hours or after every unformed stool. The recommended maximum daily dose of loperamide is 16 mg/day.
  - Continuation of loperamide is suggested until diarrhea-free for 12 hours.
  - If mild to moderate diarrhea persists for more than 24 hours, administer loperamide 2 mg every 2 hours and pursue evaluation for other treatable causes.
  - If mild to moderate diarrhea persists after 48 hours total treatment with loperamide, discontinue study drug(s) and consider initiation of second-line agents (lomotil, octreotide).

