#### **Complicated diarrhea of CTCAE Grade 3 or 4 diarrhea or Grade 1 or 2 with complicating features requires aggressive management:**

- Subject must call study site physician immediately in response to any event of severe diarrhea with or without complications as listed above.
  - Hospitalization may be required for subjects most at risk for life-threatening complications.
- Interrupt investigational products until symptoms resolve; consider reintroducing at a reduced dose (discuss with Chief Trial Investigator or designee).
- If loperamide has not been initiated, begin loperamide usage immediately at an initial dose of 4 mg followed by 2 mg every 2 hours or after every unformed stool. The recommended maximum daily dose of loperamide is 16 mg/day.

- If no improvement in severity after 24-hours of maximal loperamide dosing, subject must visit study site and be evaluated:
  - For dehydration, use intravenous fluids as appropriate.
- Antibiotic therapy should be considered in patients, who present with signs and symptoms of bacterial diarrhea such as fever, bloody diarrhea, and presence of fecal leukocytes. Investigators should have a low threshold to start such treatment in patients with Grade 3 or Grade 4 neutropenia.
- Before initiation of antimicrobial therapy, stool cultures should be obtained. When bacterial etiology for diarrhea is suspected, study-treatment and anti-motility agents (loperamide or others) should be held.
- Intervention should be continued until diarrhea free for 24 hours.

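### Section 7.6.3 tells sites to discontinue pazopanib, with no restart step, for uncomplicated Grade 1-2 diarrhea that outlasts 48 hours of loperamide, a more final action than it gives for severe or complicated diarrhea

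*Protocol*

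**What the plan says.** Protocol Section 7.6.3 divides diarrhea into two categories. The milder one is defined under Table 4: "Uncomplicated diarrhea is considered mild to moderate and is defined as CTCAE Grade 1 to 2 with no complicating signs or symptoms". The complicated category is Grade 3 or 4, or Grade 1 or 2 with a listed complicating sign such as sepsis, dehydration or obvious bleeding.

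For the uncomplicated category the guidance runs through hydration, a possible dose reduction at Grade 2, diet, loperamide, and more frequent loperamide after 24 hours. The last step is "If mild to moderate diarrhea persists after 48 hours total treatment with loperamide, discontinue study drug(s"), together with considering second-line antidiarrheals. Nothing is said about restarting pazopanib.

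For the complicated category the instruction is "Interrupt investigational products until symptoms resolve; consider reintroducing at a reduced dose (discuss with Chief Trial Investigator or designee"). Where a bacterial cause is suspected, "study-treatment and anti-motility agents (loperamide or others) should be held".

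Table 2 (Section 7.6.1) has a general row, "Other Clinically Significant Adverse Events". Under it Grade 1 continues, clinically significant Grade 2 or 3 is interrupted and restarted 200 mg lower, and Grade 4 is "Discontinue IP and continue follow-up per protocol".

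**The concern.** A site that follows the uncomplicated pathway to the letter takes a patient with mild to moderate diarrhea off drug and finds no route back. A patient at the same site with Grade 3 diarrhea, or with Grade 1 diarrhea plus dehydration, may return to treatment. Another site, reading the same sentence as a hold, would restart its patient.

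At stake are avoidable loss of drug in patients with tolerable toxicity and inconsistent dosing between centres in two countries. Section 7.6.3 itself says that diarrhea on pazopanib is mainly Grade 1 or 2, so the sentence lies on the pathway for the commonest grades.

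**Working it through.** No arithmetic on alpha, power or sample size applies. The check has two parts: compare the instructions, then see how the protocol uses the two verbs elsewhere.

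**Step 1. The instructions side by side**

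| Situation | Where | Pazopanib action | Way back to drug |
|---|---|---|---|
| Uncomplicated Grade 1-2, persisting after 48 h of loperamide | Section 7.6.3 | Discontinue | None stated |
| Grade 3-4, or Grade 1-2 with complications | Section 7.6.3 | Interrupt | Reduced-dose reintroduction may be considered |
| Other clinically significant AE, Grade 2-3 | Table 2 | Interrupt | Restart 200 mg lower |
| Other clinically significant AE, Grade 4 | Table 2 | Discontinue | None stated |

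The subsection on alternative antidiarrheals that follows does mention a dose reduction once diarrhea is controlled. That sentence comes straight after the Lomotil dose and concerns Lomotil, so it does not supply the missing step.

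**Step 2. Use of *discontinue* in Tables 2 and 3** (instructions about pazopanib only)

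- Table 2, ten entries: refractory hypertension; QTc of 500 msec or more; proteinuria recurring at the lowest dose; Grade 2 pulmonary or GI bleed; Grade 3-4 or recurrent bleed; Grade 4 venous thrombosis or PE; any arterial event; thrombocytopenia unresolved or recurrent; palmar-plantar Grade 3; other AE Grade 4.
- Table 3, two entries: recurrent aminotransferase elevation after re-challenge; ALT elevation with raised bilirubin or hypersensitivity.

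Total 10 + 2 = 12, with a restart step in 0 of 12. The proteinuria entry is typical: it applies when "the Pazopanib dose can no longer be reduced, discontinue Pazopanib and continue follow-up per protocol". Nine of the 12 mention continued follow-up, one (recurrent aminotransferase elevation) says the stop is permanent, and two (palmar-plantar Grade 3 and ALT with bilirubin or hypersensitivity) say neither: 9 + 1 + 2 = 12. The second of those two stands under a stopping-criteria label, so the bare verb is used for a terminal stop at least there.

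**Step 3. Use of *interrupt* or *hold* in the same tables**

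- Table 2, nine entries: hypertension scenarios B and C; proteinuria; Grade 1 hemoptysis; other Grade 2 bleed; Grade 3 venous thrombosis; Grade 3-4 thrombocytopenia; palmar-plantar Grade 2; other AE Grade 2-3.
- Table 3, one entry: first ALT above 8 x ULN.

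Total 9 + 1 = 10. Nine have a restart or reintroduction step, for example palmar-plantar Grade 2: "Upon resolution to Level 1 or better restart IP with a dose reduction to 400 mg". The tenth, hemoptysis, is referred to the study physician.

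**Step 4. Sensitivity of the count to classification**

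- Counting the suggestion to consider discontinuation under palmar-plantar Grade 2 gives 0 of 13 instead of 0 of 12.
- Leaving out hypertension B, which is also only a suggestion to consider, gives 8 of 9 instead of 9 of 10.
- Treating the first ALT event as a physician referral, because re-challenge there also requires contact, gives 8 of 10, or 7 of 9 with hypertension B left out as well.

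Under every version *discontinue* is never followed by a restart, and every interruption leads to a restart step or a referral.

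**The case against.** The strongest objection concerns timing. A reader might infer that Section 7.6.3 simply inverts the severity order. The text does not support that. In the uncomplicated pathway the stop is the last rung, reached only after loperamide has failed for 48 hours; until then the patient stays on drug. In the complicated pathway the interruption is immediate and hospitalization may follow, so early on that pathway is the stricter one. It also gives no separate drug action for complicated diarrhea that persists despite loperamide. Persistence under treatment and grade are different axes. This objection stands and narrows the defect to a terminal verb with no restart step.

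A reader might also infer that permanent discontinuation is mandated. That is not certain. Section 6.3.1 does not list this event as a reason for permanent discontinuation, counts toxicity there by investigator judgement, and says that a temporary interruption for an AE is not permanent discontinuation. Section 7.6.3 describes itself as general guidance that does not displace clinical judgment. The sentence sits beside starting second-line antidiarrheals, which suits a hold, and it lacks the follow-up or permanence wording that 10 of the 12 table entries carry. These points make a hold plausible. They do not settle it: no text says a hold is meant, and where Section 7.6.3 clearly means a temporary stop it uses other verbs.

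Finally, Grade 4 is not a safe comparator. If Table 2's general row governs Grade 4 diarrhea, that event is also discontinued. The contrast is firm for Grade 3 and for complicated Grade 1-2.

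**Conclusion.** The point holds as a minor internal inconsistency. Taken literally, and in line with how Tables 2 and 3 use the verb, the protocol gives persistent mild to moderate diarrhea a terminal stop that it does not require for worse diarrhea. Since a hold may have been intended, the practical risk is that sites diverge.

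The conclusion rests on two assumptions: that sites read *discontinue* here as they would in the tables, and that no supplementary site instruction outside the documents resolves it.

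The documents give no frequency for uncomplicated diarrhea lasting beyond 48 hours of loperamide, so the number of patients affected is unknown and may be small. A reader might infer harm to the primary analysis. The documents do not show it: Section 10.1.1 defines success as being alive and progression free at 12 weeks, and Section 5.7 continues imaging after drug is stopped in patients who have not progressed, unless new anti-cancer therapy starts. No effect on the primary endpoint, power or error rates is claimed.

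**What to change.** In the uncomplicated pathway of Section 7.6.3, replace the instruction to discontinue with: *interrupt study drug(s) until symptoms resolve, then restart, considering a 200 mg reduction.* This uses the resolution criterion already given for complicated diarrhea and the 200 mg step in Section 7.6.1.

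Do not add a general note to Table 2 sending all diarrhea to Section 7.6.3. That would move Grade 4 diarrhea from Table 2's discontinuation rule to interruption with possible reintroduction, a looser safety rule that nothing here justifies. If a cross-reference is wanted, limit it to uncomplicated Grade 1-2 diarrhea.

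One existing ambiguity would carry over to long interruptions: Section 6.3.1 lists a delay of more than 3 weeks as a reason for permanent discontinuation, while Section 7.6.1 allows resumption after more than 21 days on review by the Chief Investigator. The edit neither creates nor resolves this.

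The cost is one sentence in the next amendment, with no added procedures, visits or patients.

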#### **Complicated diarrhea of CTCAE Grade 3 or 4 diarrhea or Grade 1 or 2 with complicating features requires aggressive management:**

- Subject must call study site physician immediately in response to any event of severe diarrhea with or without complications as listed above.
  - Hospitalization may be required for subjects most at risk for life-threatening complications.
- Interrupt investigational products until symptoms resolve; consider reintroducing at a reduced dose (discuss with Chief Trial Investigator or designee).
- If loperamide has not been initiated, begin loperamide usage immediately at an initial dose of 4 mg followed by 2 mg every 2 hours or after every unformed stool. The recommended maximum daily dose of loperamide is 16 mg/day.

- If no improvement in severity after 24-hours of maximal loperamide dosing, subject must visit study site and be evaluated:
  - For dehydration, use intravenous fluids as appropriate.
- Antibiotic therapy should be considered in patients, who present with signs and symptoms of bacterial diarrhea such as fever, bloody diarrhea, and presence of fecal leukocytes. Investigators should have a low threshold to start such treatment in patients with Grade 3 or Grade 4 neutropenia.
- Before initiation of antimicrobial therapy, stool cultures should be obtained. When bacterial etiology for diarrhea is suspected, study-treatment and anti-motility agents (loperamide or others) should be held.
- Intervention should be continued until diarrhea free for 24 hours.

### **Alternative Pharmacologic Intervention for Uncomplicated and Complicated Diarrhea**

- Lomotil (dephenoxylate 2.5 mg + atropine 0.025 mg) can be used. The recommended dose is 2 tablets 4 times daily. When diarrhea is under control, a dose reduction should be attempted.

### **Nausea and Vomiting**

Every attempt should be made to control nausea and vomiting in subjects who have emesis and are unable to retain Pazopanib.

Routine pre-medication for nausea is not necessary, but symptomatic subjects should be treated with standard anti-nausea/anti-emetic therapy as necessary.

If a subject vomits after taking study medication, the subject should be instructed not to take a replacement dose on that same day. The subject should resume taking Pazopanib at the next scheduled dose on the following day. If vomiting persists, then the subject should contact their physician. To prevent or treat nausea and vomiting standard medications are recommended. Depending upon approved medications in your region, these may include: 5-HT3 receptor antagonist (granisetron, ondansetron, dolasetron mesylate); NK-1 receptor antagonists such as aprepitant, metoclopramide, phenothiazine (prochlorperazine); corticosteroids, (dexamethasone, prednisone); and cannabinoids (dronabinol).

## 8. STUDY ASSESSMENTS AND PROCEDURES

### 8.1. Study Development

Screening test for inclusion (lab tests and imaging) should have been performed  $\leq$  14 days before first dose administration.

**Table 5:** summarizes the assessments to be performed throughout the study as well as their schedule.

## TABLE Of ASSESSMENT

	Before Treatment	During Treatment											After treatment		
		Week 0	W1	W3	W5	W7	W9	W 12	Every 4 weeks (after w12)	Every 8 weeks	Every 12 weeks	28 days after end of treatment	Before PD, every 8 weeks until PD	After PD every 12 weeks	
		Day 1	Day 8	Day 22	Day 36	Day 50	Day 64	Day 85							
Informed Consent	X														
Inclusion/Exclusion Criteria	X														
Medical history	X														
Physical Exam a (with vital and cancer signs and symptoms)	X	X	X	X	X	X	X	X	X	X		X	X		
ECOG	X	X	X	X	X	X	X	X	X	X			X		
Concomitant Medication	X	X	X	X	X	X	X	X	X	X					
Clinical Laboratory Tests b,c	X	X	X	X	X	X	X	X	X	X		X			
ECG d	X					X		X		X		X			
LVEF (MUGA/ECO)	X **							X				X			
Efficacy Assessment (Imaging/MRI) *	X **					X		X		X			X		
Adverse Events			X	X	X	X	X	X	X	X		X			
Tumor specimen collection 	X														
Serum collection 	X			X											
Treatment control and dispensing		X		X	X	X	X	X	X	X					
Survival															

\*Tumor assessment should be repeated in week 7 and week 12 and every 8 weeks thereafter until documented progression for patients with CR, PR, or SD and/or for patients who have discontinued study therapy due to toxicity or reasons other than progressive disease, unless they have started a new anti-cancer therapy.

\*\*Both tumor assessment before treatment and LVEF can be done up to 28 days prior the start of the treatment.

 Tumor sample will be collected before treatment.

Serum will be collected as described:

1. Within 72 hours prior starting the treatment (basal).
2. Within 72 hours after first 3 weeks of treatment (day 22).
3. Within 72 hours after radiological response is documented.
4. Within 72 hours after progressive disease is documented.

 Monitoring of BP: A measurement of BP should be taken the day of the visit +/- 3 days.

 Hematology Profile and Chemistry Profile (including liver Function) in every visit

 Thyroid function test (T4 and TSH):basal and every 12 weeks.

 ECG: Baseline, week 7 and 12 and every 8 weeks thereafter.

Unless otherwise indicated, during treatment the marge for visits / explorations is +/- 4 days and after completion of treatment +/- 7 days

